1. INTRODUCTION

1.1. Background

Cystic fibrosis (CF) affects approximately 100,000 people worldwide {Dmitrienko et al 2003}. CF is the most common life-shortening genetic disorder in Caucasians, with a median age of death of 27.5 years in the US {Boyle 2007, Cystic Fibrosis Foundation 2013} and 28.0 years in the EU {European Cystic Fibrosis Society 2010}. CF is an autosomal recessive disorder characterized by progressive, obstructive pulmonary disease. Patients with CF are particularly susceptible to chronic airway infections with opportunistic bacteria such as *Staphylococcus aureus*, *Haemophilus influenzae*, *Pseudomonas aeruginosa* (PA), *Stenotrophomonas maltophilia*, *Achromobacter* species, and *Burkholderia* species.

The majority (70%) of patients with CF die of cardiorespiratory failure {Foundation 2010}. This is the end result of a continuous cycle of airway obstruction, inflammation, and infection leading to bronchiectasis, parenchymal destruction, and loss of pulmonary function {Gibson et al 2003}. Patients also experience episodes of acute pulmonary exacerbation, which is characterized by worsening respiratory symptoms and an acute decline in lung function.

The current standard of care in CF includes treatment with inhaled anti-pseudomonal antibiotics (eg, tobramycin and Cayston[®]) and mucolytics (eg, dornase) {Mogayzel et al 2013}. Recently 2 CF transmembrane conductance regulator (CFTR) modulator therapies have been approved for treatment of CF patients with select genetic mutations. Ivacaftor (Kalydeco[®]) {Davies et al 2013, Ramsey et al 2011} has been approved for CF patients who carry one of the G551D CFTR gating mutations. The other is a combination product combining ivacaftor with lumacaftor for CF patients who are homozygous with the most common CF mutation, F508del. Both drugs improve lung function and reduced pulmonary exacerbations. While current CFTR modulator therapies provide clinical benefit to almost 50% of the CF population, the therapy does not represent a complete clinical cure.

1.2. GS-5745

1.2.1. General Information

For further information on GS-5745, refer to the Investigator's Brochure (IB) for GS-5745.

1.2.2. Preclinical Pharmacology and Toxicology

GS-5745 is a humanized high-affinity monoclonal IgG4 antibody that is a selective and potent allosteric inhibitor of matrix metalloproteinase 9 (MMP9). In CF patients, sputum MMP9 levels are 13- to 14-fold higher in sputum to 100-fold higher in bronchoalveolar lavage (BAL) than that of healthy controls at Baseline and during CF exacerbations, respectively {Bergin et al 2013, Hahn et al 2012}. Murine surrogates of GS-5745, with similar epitope specificity and inhibitory activity, have demonstrated significant anti-inflammatory and tissue-protective activity in rodent models of ulcerative colitis (UC) and rheumatoid arthritis (RA). Unlike pan-MMP inhibitors,

specific inhibition of MMP9 with a murine surrogate of GS-5745 showed no evidence of inducing musculoskeletal symptoms or pathology in a rat model. In addition, there were no effects on safety pharmacology endpoints (clinical observations, electrocardiograms, respiratory rate) in the 4-week repeat-dose toxicity studies at doses of up to 100 mg/kg/dose.

The toxicology program consists of completed 4-week and 26-week repeat-dose IV toxicity studies in both rats and monkeys and a human tissue cross-reactivity study. To support the transition to a SC formulation, a SC local tolerability study in rats was conducted and the 26-week toxicity studies in rats and cynomolgus monkeys included both IV and SC routes. Rat and rabbit embryo fetal development studies and a rat fertility study have also been completed. As expected, there was no specific GS-5745 staining observed in normal human tissues. At doses of GS-5745 up to 100 mg/kg/dose IV, data indicate no test article-related maternal or fetal effects in rats and rabbits, and no test article-related effects on male or female fertility in rats. Findings associated with GS-5745 treatment in the 4-week repeat-dose toxicity studies have been limited to reversible physal hypertrophy in rats, an expected response to MMP9 inhibition, and reversible increased adrenal gland weight in female monkeys at all doses, which was associated with slight hypertrophy of the zona fasciculata in a single 100-mg/kg/dose female monkey. In the 26-week studies, there were no findings of toxicological concern in rats or cynomolgus monkeys following weekly IV or SC administration at doses up to 100 mg/kg/dose and 150 mg/kg/dose, respectively. The lack of physal hypertrophy observed in the rat 26-week study is presumably due to the reversible nature of this finding as longitudinal bone growth and growth plate closure slows/completes. There were no adverse injection site reactions observed in the 26-week studies, and no adverse findings in the local tolerability study.

The NOAEL in the rat and monkey 26-week studies was 100 mg/kg/dose IV and 150 mg/kg/dose SC, the highest doses evaluated by each route of administration in each study. The maximum proposed SC clinical dose of approximately 10 mg/kg [600 mg (4 x 150 mg/ml injections) to a 60 kg patient] is 15-fold lower than the high SC dose in the 26-week toxicity studies.

Therefore, the toxicology studies support the proposed SC dose, dose regimen, and the duration of the clinical study. Overall, the nonclinical program has demonstrated that GS-5745 has the potential to be a safe and effective therapy for controlling the inflammation and tissue damage associated with CF. A more detailed description of the nonclinical program is provided in the IB.

1.2.3. Clinical Trials of GS-5745

In addition to the clinical development program in CF, GS-5745 is being developed for the treatment of solid tumors, UC, RA, and chronic obstructive pulmonary disease (COPD). At least 221 subjects have been enrolled in clinical studies evaluating GS-5745. Details of the clinical studies in these diseases can be found in the IB.

A Phase 1 study of GS-5745 administered IV (up to 5 mg/kg GS-5745 every 2 weeks) or SC (150 mg GS-5745 weekly) in patients with moderately to severely active UC demonstrated clinical activity at Day 36 and low rates of AEs were observed. Additionally, immunohistochemistry and RNA sequencing provided supportive evidence of the biological activity of GS-5745 {[Bhandari et al 2015](#)}.

In a Phase 1 study of GS-5745 (with doses up to 1800 mg IV every 2 weeks) alone and in combination with chemotherapy in patients with advanced solid tumors, preliminary safety data demonstrated a manageable safety profile. There were no observed responses in the monotherapy escalation phase. However, when combined with chemotherapy in the expansion phase in subjects with measurable target lesions there were objective response rates of 64% (7/11) and 41% (7/17) for esophagogastric and pancreatic cancers respectively {[Bendell et al 2015](#)}.

GS-5745 has also been studied in RA. A total of 18 subjects (15 active: 3 placebo) with active RA documented by a mean Screening CRP value of ≥ 8.0 mg/L received 400 mg of GS-5745 or placebo every 2 weeks for a total of 3 infusions. Subjects continued their routine RA medical regimen during the study, but the use of biologics was prohibited. All subjects had baseline moderate to high disease activity assess by Disease Activity Score (DAS28-CRP) and completed the study. At Day 43 the proportion of subjects that achieved either low disease activity or remission in the GS-5745 and placebo groups were 4/15 (27%) and 0/3 (0%) respectively.

Highlighting FEV₁ results of the Phase 1 COPD study (8 active: 3 placebo), of the 6 subjects that received 400 mg IV every 2 weeks for a total of 3 infusions, 2 of 6 subjects demonstrated mean absolute improvement in FEV₁% of 8.6% and 6.6% respectively. Changes in FEV₁ in the 2 placebo subjects that also completed 3 doses over the same time course were <4.0%. Though the sample size is small and study duration brief, it suggests GS-5745 may be able to positively affect FEV₁ in respiratory indications.

To date there has been no study drug-related adverse safety signal observed in any of the completed or active studies in any of the indications under clinical development with GS-5745 (oncology, UC, Crohn's disease, RA, COPD).

1.3.1. Route of Administration

The highest safe and practical dose of GS-5745 will be administered in Part 1 of the study to maximize the likelihood of observing a clinical effect on the primary endpoint, FEV₁. As of 07 Dec 2015 GS-5745 has been administered to 221 subjects in several Phase 1 studies in oncology, UC, RA, and COPD and in Phase 2 studies in UC and Crohn's disease. The majority of dosing with GS-5745 has been with an IV formulation with up to 1800 mg every 2 weeks as the highest dose safely administered to oncology subjects. While a short-term IV study with GS-5745 may be achievable in CF, feedback from CF experts suggests that long-term chronic IV treatment with GS-5745 would be difficult and the preferred route would be SC. Thus, this proof-of-concept study will use a SC formulation.

1.3.2. Dose Selection

The GS-5745 SC formulation currently available for clinical studies is a pre-filled syringe at a concentration of 150 mg/mL. To investigate the highest, safe and practical SC dose of GS-5745 for this study, single and multiple SC injection regimens were considered. Weekly SC dosing of 600 mg GS-5745 is expected to be safe in CF patients. Taking into consideration that the bioavailability of the SC formulation of GS-5745 is approximately 44%, this CF dosing regimen would translate to a bimonthly dose of approximately 528 mg which is below the proposed Phase 3 oncology study in gastric adenocarcinoma of 800 mg IV Q 2 weeks and similar to the fixed dose IV dosing of 400 mg every 2 weeks in the Phase 1 RA and COPD studies. As of 25 September 2015 review of the safety data of GS-5745 in all current indications (oncology, UC, Crohn's disease, RA, and COPD) no adverse safety signal has been observed. Moreover, no increased risk of infections or sepsis has been noted despite the use of chemotherapy or immunosuppressive agents in the oncology, UC, Crohn's and RA studies. Thus, the body of GS-5745 safety data suggests that dosing 600 mg SC weekly in CF subjects should not pose an unreasonable risk for serious adverse events.

To determine potential range of MMP9 concentrations as well as binding to GS-5745 in sputum of CF subjects, *in vitro* mixing experiments were performed. Sputum samples from six distinct CF patients with stable disease were evaluated. The mean MMP9 concentration was ~2600 ng/ml (~28.3 nM), spanning 570-3700 ng/ml (6--40 nM), across these six sputum samples. After mixing varying concentrations of GS-5745 into each sputum sample, free MMP9 and GS-5745-bound-MMP9 were measured using an enzyme-linked immunosorbent assay (ELISA). On average, 1:1 binding was observed between MMP9 and GS-5745, establishing stoichiometric binding of GS-5745 to MMP9 in sputum. Stoichiometric binding is expected based on the K_D of GS-5745 for MMP9 and the knowledge that MMP9 complex formation (with TIMP, NGAL, etc.) does not interfere with GS-5745 binding.

To best predict a dose that achieves a GS-5745 concentration in molar excess of sputum MMP9, we considered both the previously-observed GS-5745 pharmacokinetics and CF-specific factors that may influence pharmacokinetics. Subcutaneous dosing of GS-5745 has been studied in UC using a 150 mg/ml formulation in a prefilled syringe. Weekly dosing of one 150 mg SC injection for 4 weeks has demonstrated clinical efficacy in a Phase 1 study, and Phase 2 studies are underway in UC and Crohn's disease using the SC formulation. Baseline mean total plasma MMP9 concentrations in the Phase 1 UC studies were found to be 143.09 ng/ml with the maximum value being 1279.40 ng/ml (N=50 (Gilead, data on file)). In contrast, total plasma MMP9 concentrations in CF appear to be much higher with a mean of approximately 670 ng/ml and a maximum value of > 1500 ng/ml (N=19) {Hahn et al 2012} using the same ELISA. These findings suggest that the total body MMP9 load is greater in CF than in UC. The relative increase of MMP9 in CF to UC may be 4 to 5-fold. Thus, to account for a potentially larger MMP9 antigen sink in CF, subjects will receive a 4.0-fold higher dose in CF, or 600 mg (4 SC injections [1 mL/injection] of GS-5745 [150 mg/ml] weekly) in Part 1 of this study.

Pharmacokinetic modeling provides further rationale for weekly SC dosing of 600 mg GS-5745. Plasma PK of GS-5745 in CF subjects was predicted based on preliminary population PK modeling results in UC patients, assuming a 5-fold higher target-mediated drug clearance in CF than in UC subjects based on higher plasma MMP9. GS-5745 levels in sputum were assumed to be 10% of plasma concentrations in CF subjects, based upon an approximate 1 log reduction between serum and sputum IgG₄ in patients with non-CF bronchiectasis {Hill et al 1998}, a surrogate for CF. The projected C_{max} and C_{min} of GS-5745 in sputum are 2.4 µg/mL (16.3 nM) and 0.02 µg/mL (0.14 nM) after the 1st 600 mg injection, and 7.1 µg/mL (48.4 nM) and 3.1 µg/mL (21.1 nM) after the last injection, respectively, in majority of CF subjects. Based on the approximately 1:1 binding observed in the *in vitro* sputum mixing studies, the 600 mg SC weekly dosing is expected to achieve consistent binding to MMP9 in the sputum in the >75% of CF patients. Correspondingly, 300 mg and 150 mg SC weekly dosing are expected to achieve lower fractional binding of MMP9 in sputum for shorter durations than the 600 mg SC weekly dosing.

1.3.3. Study Duration

Clinical improvement has been observed within 5 weeks of weekly SC dosing of GS-5745 in Phase 1 UC studies. A possible mechanism for this rapid response is that GS-5745 is a high affinity antibody with picomolar potency that targets MMP9 directly at the site of inflammation/tissue damage. The rapid clinical improvement may be due to the inhibition of upregulated MMP9 in affected regions of the colon. It is hypothesized that an 8-week period of treatment with GS-5745 may lead to further clinical improvement than the 5-week endpoint in the Phase 1 UC studies.

It is uncertain if the clinical response timeframe seen in the UC Phase 1 studies can be extrapolated to CF. A study employing the anti-inflammatory ibuprofen, known to improve FEV₁ in CF with chronic therapy {Konstan et al 1995} failed to demonstrate a clinical improvement in FEV₁ after only a 4 week treatment course {Chmiel et al 2015}. To increase the likelihood of observing an improvement in FEV₁ in this study, an 8-week dosing period will be

used paralleling the 8-week induction regimen planned for the Phase 2 UC study. If the results of Part 1 of this study are positive, then 2 lower doses, 300 mg and 150 mg, will be studied in Part 2 of the study.

1.4. Risk/Benefit Assessment for the Study

GS-5745 is currently being evaluated in 5 ongoing clinical studies for the treatment of solid tumors, UC, Crohn's Disease, RA, and COPD. From the adverse events reported in these trials none have been identified as adverse drug reactions causally related to the drug. Also, no drug interactions or contraindications have been reported.

Potential risks may include local injection site reactions and the rare possibility of hypersensitivity or allergic reactions which have been reported with the use of biologics. A single hypersensitivity reaction was observed after a second infusion in a UC subject. The subject was evaluated at the local emergency room and was discharged home in satisfactory condition. Despite this single hypersensitivity reaction after an IV infusion of GS-5745, it should be noted that GS-5745 is not considered to be a 'high risk' agonist as it acts by antagonism and targets MMP9. However, to mitigate the potential risk associated with SC administration of GS-5745, subjects will be monitored for 120 minutes after first SC injection and for 30 minutes after all subsequent SC injections of each dose during the blinded phases of Part 1 and Part 2 of the study. To be prepared for a theoretical risk of a systemic injection site reaction, study sites will be required to have on site and readily available, injectable epinephrine. Home health provider's administering the at home injections will also have readily available an auto-injectable form of epinephrine. Prior to administering drug, clinic staff and the home health provider will review the clinical manifestations of anaphylaxis and the proper use of the auto-injectable epinephrine. Unless there is an adverse event safety signal of concern observed with SC injections in the blinded phases of Part 1 and Part 2, within OLE study subjects will be monitored for 120 minutes after the first SC injection and for 30 minutes after the second SC injection. For subsequent SC injections in the OLE, subjects will be monitored for at least 15 minutes after each injection.

Only patients who are on stable CF medication regimens from 30 days prior to Baseline and throughout the duration of the study will be eligible to enroll therefore the impact on the patients' habitual standard of care should be negligible.

Despite many advances in CF therapies, the majority of CF patients experience progressive loss of lung function and recurrent exacerbations. Compared with healthy controls, patients with CF have MMP9 concentrations 13- to 14-fold higher in sputum and 100-fold higher in bronchoalveolar lavage (BAL) samples {[Bergin et al 2013](#), [Devereux et al 2014](#), [Hahn et al 2012](#)}. Dysregulated MMP9 in CF has been postulated to augment proteolytic damage to lung parenchyma, enhance IL-8 activity, and release chemotactic peptides such as PGP {[Gaggari et al 2007](#)}. Excess airway MMP9 is associated with reduced lung function {[Sagel et al 2005](#)} and acute exacerbations in CF patients {[Roderfeld et al 2009](#)}. Therefore, treatment with GS-5745 may reduce airway MMP9 activity in patients with CF and result in reduced airway inflammation and stabilization and/or improvement in lung function.

This clinical study will provide information about the benefits GS-5745 may have in the CF population and potentially provide an additional therapy to improve the health and life-expectancy of patients living with this life-limiting condition. These benefits are believed to outweigh any potential risks, particularly in the context of this clinical trial.

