3.3.3. Open-Label Extension (OLE)

On the Week 8 visit (-3 to + 4 days) of both Part 1 and Part 2, subjects (active and placebo) will be invited to participate in an OLE treatment period.

- Subjects choosing to participate from Part 1 will receive open-label 600 mg of GS-5745 weekly for 16 additional weeks.
- All subjects choosing to participate from Part 2 will receive open-label 300 mg of GS-5745 weekly for 16 additional weeks.

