5.3. Dosage and Administration of GS-5745 and Placebo

GS-5745 or placebo for SC injection will be administered to subjects on the thighs, the stomach area (abdomen), or the deltoid area of the upper arms in the blinded phase of the study. In the OLE if self-injection at home is determined to be safe, deltoid injections will not be allowed. If the abdomen area is chosen, the area 5 cm (2 inches) around the umbilicus should be avoided. GS-5745 or placebo will be administered SC at the research center at study visits during the blinded phase of the study. If the dose requires multiple SC injections, all injections should be delivered within 1 hour. The investigator or a qualified designee must be present during the administration during the blinded phase of the study.

In the blinded phase of the study, if the subject has a body temperature of > 38°C (100.4°F), his/her FEV₁ % predicted is less than 40% or his/her FEV₁ % predicted decreases by > 30% from Baseline on study site visits requiring spirometry, AM pre-bronchodilator PEF decreases by >30% from the mean PEFR obtained during Screening during non-spirometry visits, or in the medical opinion of the investigator or home health provider the subject is unfit to receive study drug at a given visit, the subject should not be administered study drug. In consultation with the medical monitor, the Investigator may delay dosing until the parameters above are met. See Section 6.3.6 for additional information on the spirometry measures.

During the OLE portion of the study subjects will have the option to continue to receive study drug SC injections at their respective study clinic receive SC injections by a qualified home health provider (where available) at their residence in the short-term with the long-term plan to eventually self-administer the study drug without supervision at home after the DMC and Gilead have reviewed safety data and agree home administration appears safe. At the beginning of the

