- f Chest x-ray will be obtained during the screening period if subject does not have a CT scan, MRI or chest x-ray obtained in the 90 days prior to Baseline.
- g Spontaneous and induced sputum should be obtained AFTER spirometry and FRI (if applicable) have been completed. If spontaneous sputum cannot be obtained, a throat swab may be used for microbiology culture. A second spontaneous sputum microbiology for culture will be collected in the screening period.
- h For subjects enrolled in the FRI sub-study only. Subjects will withhold their standard of care inhaled CF therapies prior to FRI.
- i At Baseline, PK should be obtained prior to and 2 hours after study drug administration. At all other visits with study drug dosing, PK should be performed prior to study drug administration. Subjects who consent to the optional PK sub-study will have one additional single PK sample collected at Day 5 (± 1) and Day 48 (± 1). Optional Day 5 PK and Day 8 should occur at least 1 day apart.
- j Blood for CF genotyping should be taken at baseline for subjects who do not have a historical genotype on file, but may be collected at any time during the study, if necessary. Blood for optional genomic research should only be taken from subjects who consented to this optional procedure. It should be taken at baseline, but may be collected at any time during the study, if necessary.
- k Observe subject for 2 hours after study drug administration on Day 1, and for 30 minutes after study drug administration at all other visits during the blinded phase of the study.
- l The baseline/randomization visit may be split over 2 days as needed. If the visit is split over 2 days, the following procedures should be done on the first day prior to standard of care inhaled CF therapies as indicated in Section 5.5: questionnaires, urine pregnancy test (for women of childbearing potential only), oxygen saturation, pre- and post-bronchodilator spirometry, and FRI. Subjects must withhold their standard of care inhaled CF therapies again the next morning and perform spirometry prior to any remaining study procedures and study dosing. The day on which the first dose of study drug is administered is Baseline.
- m Two spirometry measures (pre-bronchodilator) taken at least 4 days apart (one during Screening, one at Baseline) must be taken to meet inclusion criterion 7.

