6.1.3. Baseline/Randomization (Day 1)

All Baseline tests and procedures must be completed prior to randomization and dosing on Day 1 as indicated in Table 6-1.

If subjects are unable to complete all Baseline assessments in a single day, the baseline/randomization visit may be split over 2 consecutive days as needed. If the visit is to be split over 2 days, the following procedures may be done on the first day and should be done prior to standard of care inhaled CF therapies as indicated in Section 5.5:

- Refer to Figure 6-1 for recommended visit schedule and order of procedures for Screening and Baseline visits.
- Sputum induction and blood draws for safety and pre-dose PK can be performed on either day of the baseline/randomization visit, but must be performed prior to study drug dosing.
- At the Baseline/Randomization visit, subjects who meet the eligibility criteria will be randomized into the study. Study drug should be administered after randomization. Subjects will be observed for 2 hours after the last injection. Blood for PK will also be obtained 2 hours after the last injection of study drug. Day 1 will be the day on which the subject receives the first dose of study drug.

6.1.4. Blinded Treatment Period: Day 5 through Week 7

At visits in the blinded treatment period, subjects should complete the CFQ-R, SNOT-22, and the TSQM prior to all other procedures when indicated in Table 6-1. At visits where study drug dosing is indicated, the subject should be observed for 30 minutes after the last injection. Subjects who provide separate consent for the PK sub-study will provide a Day 5 plasma PK sample. At the Day 48 visit blood for PK will be obtained.

For sites and subjects utilizing home health services for at home dosing of study drug, site staff should instruct the subject on the packaging, storage, self-administration, and safe needle disposal for GS-5745. Following 2 successful doses in clinic within the blinded period, the subjects and the site may choose to utilize the home health service (See Section 6.1.6 for further information). If the home health option is utilized, subjects will be dispensed GS-5745 at the visit prior to the scheduled home health visit for Weeks 3, 5, and 7 within the blinded period.

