6.1.5. Week 8 (-3 to + 4): Primary Endpoint and Open-Label Extension

All Week 8 tests and procedures must be completed prior to participating in the OLE and dosing as indicated in [Table 6-1](#).

Subjects who agree to participate in the OLE portion of the study will be entered into the IXRS to confirm enrollment into the open-label extension after all other procedures as indicated in [Table 6-1](#). The first dose of open-label GS-5745 should be dispensed as directed by IXRS and administered to the subject at Week 8. Sites should train the subject on administration of the study drug at this visit. Subjects will be observed for 30 minutes after the last injection for the first 2 doses.

If the home health option is utilized during OLE, subjects will be dispensed GS-5745 at the visit prior to the scheduled home health visit for Weeks 11, 13 to 15, 17 to 19 and 21 to 23.

Subjects who do not agree to participate in the OLE portion of the study will be discontinued from the study and will be asked to return to the clinic in 30 days for their 30-day Follow-up visit as indicated in [Table 6-1](#).

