8.12. Interim Analyses

To determine if Part 2 of the study should be initiated, an interim analysis will be conducted when all the randomized subjects from Part 1 have completed the Week 8 visit or discontinued from the study. Unblinded data from Part 1 will be used to evaluate drug safety and efficacy, which may result in a study amendment before the initiation of Part 2 of the study.

A Gilead internal unblinded team independent of the blinded study team will be assembled at the beginning of the study, which consists of medical monitor, statistical programmer, biostatistician and other personnel if necessary. The Gilead internal unblinded team will be granted the access to unblinded clinical data including treatment assignment to closely monitor study progress and drug safety. To mitigate the risks of inadvertently releasing the treatment information to the sites and subjects, the internal team will keep the unblinded information confidential and will not communicate the information to blinded study team, site staff or subjects. Data unblinding due to medical emergency will follow standard Gilead procedures.

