**Figure 1-1. Study Design Schema**

There was a FRI sub-study which required 2 FRI scans (at Baseline and at the Week 8 visit).

Up to 150 subjects with CF  $\geq$  18 years of age were planned to be enrolled.

Subjects randomized to placebo in Part 1 received 4 SC injections per dose. Subjects randomized to placebo in Part 2 would receive 2 SC injections per dose.

The study was terminated after 6 subjects were enrolled in Part 1 of the study. Therefore, Part 2 was not initiated.

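### Observation after the first open-label dose is 120 minutes in protocol Section 1.4 but 30 minutes in the Week 8 site procedure, Section 6.1.5

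*Protocol*

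**What the plan says.** Protocol Section 1.4 presents monitoring after injection as mitigation for the risks of subcutaneous dosing, having just named local reactions and hypersensitivity. For the OLE it states that "within OLE study subjects will be monitored for 120 minutes after the first SC injection and for 30 minutes after the second SC injection", with at least 15 minutes after later injections. This is the default, applying if the blinded phases show no safety signal of concern.

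Protocol Section 6.1.5 is the Week 8 procedure, under which the first open-label dose is given. Its rule is "Subjects will be observed for 30 minutes after the last injection for the first 2 doses".

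The rule for the first blinded dose is consistent across the protocol. Section 6.1.3 says "Subjects will be observed for 2 hours after the last injection", and footnote k to Table 6-1 says "Observe subject for 2 hours after study drug administration on Day 1". Footnote k is limited to the blinded phase, and the copy in SAP Appendix 1 carries the same limit. Section 6.1.7, which covers Weeks 9 to 24, gives no observation time.

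**The concern.** Both rules govern the same dose at the same visit, and nothing in the protocol or SAP says which prevails. A site working from the visit section would use the shorter one.

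The people most affected are former placebo subjects. Under Section 3.3.3, "subjects (active and placebo) will be invited to participate in an OLE treatment period". For someone randomized to placebo, the Week 8 open-label dose is the first GS-5745 received in the study: 600 mg in Part 1 or 300 mg in Part 2. The protocol asks for 2 hours of observation at the first blinded dose. Section 6.1.5 would give former placebo subjects a quarter of that (30/120) at their first actual exposure.

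Sites cannot solve this by observing only former placebo subjects for longer. Section 8.12 says the sponsor's unblinded team "will not communicate the information to blinded study team, site staff or subjects". The rule therefore has to be the same for everyone entering the OLE. What is at stake is a safety instruction; no efficacy conclusion depends on it.

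**Working it through.** The plan states no figure to reproduce. The check is whether any reasonable reading makes the two rules agree.

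**Inputs**

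| Item | Value | Source |
|---|---|---|
| First OLE dose | 120 min | Protocol 1.4 |
| First OLE dose | 30 min after the last injection | Protocol 6.1.5 |
| Second OLE dose | 30 min | Protocol 1.4 and 6.1.5 |
| Time allowed for all injections of one dose | up to 60 min ("all injections should be delivered within 1 hour") | Protocol 5.3; same limit for the OLE in 6.1.7 |
| First blinded dose | 2 hours | Protocol 6.1.3; Table 6-1 footnote k |
| Planned placebo arms | 30 in Part 1, 30 in Part 2 | Protocol 3.3.1 and 3.3.2 |
| Assumed attrition | 15% | Protocol 8.10 |

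**Both rules counted from the last injection.** First dose: 120 − 30 = 90 minutes short. Second dose: 30 − 30 = 0, so no conflict.

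**Section 1.4 counted from the first syringe.** Let s be the minutes from the first syringe to the last, with 0 ≤ s ≤ 60. Under Section 6.1.5, observation ends s + 30 minutes after the first syringe. The shortfall is 120 − (s + 30) = 90 − s:

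- s = 0: 90 minutes
- s = 30: 60 minutes
- s = 60: 30 minutes

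Even with the slowest permitted dosing, Section 6.1.5 ends 60 + 30 = 90 minutes after the first syringe, still 30 minutes early.

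**The safety-signal condition.** In Section 1.4 the 120 minutes apply when there is no signal. The condition does not permit a shorter period, and Section 6.1.5 has no matching condition.

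**Footnote k.** It covers the blinded phase only. If a site treated Week 8 as a blinded-phase visit, the footnote would give 30 minutes, so it does not restore the 120-minute rule either.

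**Subjects affected, as planned.** At most 30 + 30 = 60 former placebo subjects, or 60 × 0.85 = 51 after the assumed attrition. Both figures assume that Part 2 opened and that every eligible subject chose the OLE.

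**Subjects affected, in the event.** SAP Section 1.2 records: "The study was terminated after 6 subjects were enrolled in Part 1 of the study". Part 2 was not started. At most 6 subjects could have received a first open-label dose. At 1:1 allocation about 6 × 1/2 = 3 would have been on placebo; this is an assumption, since the documents do not give the split.

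**The case against.** The strongest reply is that the two rules can both be met. Section 6.1.5 sets no upper limit, so a site observing for 120 minutes complies with both sections, and Section 9.1.9 holds the investigator to the whole protocol. That is true, but it requires the site to go beyond the visit instruction on the strength of a background section.

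Other safeguards exist. Section 1.4 requires injectable epinephrine on site and a review of the signs of anaphylaxis before dosing. The Week 8 dose is given at a clinic visit. The one hypersensitivity reaction reported followed a second intravenous infusion, not a first subcutaneous dose. These points lower the risk but leave the contradiction in place.

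Sites may also have had the right time in the study procedures manual or the Pharmacy Manual, which are not among the documents. The mismatch in the protocol is therefore certain, while what sites actually did is unknown.

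Section 1.4 says *injection* where a dose is 2 or 4 syringes. If its first injection meant the first syringe of every dose, the second dose would conflict as well. That reading is strained: Section 1.4 contrasts the first, second and subsequent injections across the OLE, which fits doses.

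Finally, the study has ended and few subjects were enrolled. This limits the consequence. It does not make the protocol text correct.

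**Conclusion.** The inconsistency is real and confined to the first open-label dose. Section 6.1.5 falls 90 minutes short of Section 1.4 on a common start point, and 30 to 90 minutes short if Section 1.4 runs from the first syringe. This rests on reading the first and second injections in Section 1.4 as the first and second doses.

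It should be corrected because a stated safety measure is contradicted in the section sites follow, at the visit where former placebo subjects first receive GS-5745 in the study. The realised effect is small: at most 6 subjects, and fewer if some did not reach Week 8 or declined the OLE, neither of which the documents report.

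**What to change.** Replace the observation sentence in Section 6.1.5 with:

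> Subjects will be observed for 120 minutes after the last injection of the first open-label dose and for 30 minutes after the last injection of the second.

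Counting from the last injection satisfies Section 1.4 whether its 120 minutes start at the first or the last syringe, and it matches the Day 1 rule in Section 6.1.3. Footnote k to Table 6-1 needs no change. The 15-minute minimum for later open-label injections appears in neither Section 6.1.5 nor Section 6.1.7. That is a separate omission, but it could be added in the same edit.

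The cost is up to 90 more minutes at one clinic visit for each OLE subject, including former active subjects who have already tolerated the drug. There is no statistical cost. Since dosing in this trial has ended, the practical value lies in any later protocol that reuses this text.
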